1.4 Preliminary Data

N/A

1.5 Sample Size Justification

We anticipate a sample size of 20 subjects, 10 subjects in the *Eucalyptus globulus* group and 10 subjects in the *Mentha x piperita* group. This is based on previous studies which have investigated interventions for perceived muscle soreness and utilized a similar sample size for a power of 80% and a 1 tailed level of significance of p<0.05. [15]

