1.0 Research Design

1.1 Purpose/Specific Aims

The purpose of this study is to find an alternative, low risk option for managing muscle soreness in the older adult and elderly population.

A. Objectives

This study aims to compare how the topical application of essential oils *Eucalyptus globulus* and *Mentha x piperita* impact delayed onset muscle soreness after eccentric exercises compared to one another and to control.

B. Hypotheses / Research Question(s)

It is hypothesized that application of *Eucalyptus globulus* or *Mentha x piperita* oil will reduce perceived muscle soreness in subjects compared to control.

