1.3 Research Design and Methods

This study is designed as a randomized controlled interventional study with a rolling enrollment over the course of 6 months, with each individual subject's participation spanning over 72 hours. 20 subjects will be recruited for participation. 10 subjects will be included in the *Eucalyptus globulus* intervention group, and the remaining 10 will be placed in the *Mentha x piperita* group. A blocked randomisation list will be generated using an online randomizer in order to allocate subjects to each treatment group randomly. Each subject will have one upper extremity serving as the control, and one upper extremity which receives the intervention.

A. Research Procedures

Subjects

Subjects 50 years old and above with no previous resistance training sessions within the past year will be recruited at The Manor Health and Rehabilitation, a subacute rehabilitation and long-term care facility. A verbal explanation will be provided to the potential subjects by [name] or [name] on-site at the facility, including the fact that their care at the facility will not be affected by their decision to participate or not, and if they are interested in proceeding they will be asked to complete a survey regarding the subject's demographics (gender, age, hand dominance), ensure there are no hypersensitivities to the oils being used, upper extremity injuries within 1 year, and that they have the functional capacity for exercise of 3.5 metabolic equivalents or greater based on the Duke Activity Status Index. Subjects will be required to sign a consent to participate in screening. If participants pass the screening process they will again be informed of the study and all potential risks/benefits prior to signing an informed consent to partake in research.

Materials

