Subject outcomes will be based on a self-reported visual analog scale, which has previously been shown to have validity in subjectively quantifying perceived muscle soreness and used in prior studies. [14,16]. These outcomes will be recorded by investigators for both the intervention and control upper extremity at 24, 48, and 72 hours post-exercise.

C. Study Duration

Each subject will participate in this study for 72 hours. The overall study is anticipated to take place over a six month duration.

D. Endpoints

The primary endpoint will be a self-reported perceived muscle soreness using a visual analog scale. There are no secondary endpoints.

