6.0 Data Management Plan

6.1 Data Analysis

Treatment analysis will involve a 1-way repeated measures ANOVA. Differences will be considered significant when p values are below an alpha level of 0.05.

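### The only power figure (80%, one-tailed 0.05, taken from earlier studies) does not apply to the non-directional ANOVA in 6.1, so actual power is unknown, and oil versus oil has no term in that model

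*Combined protocol and SAP*

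**What the plan says.** Section 1.5 sets 20 subjects, 10 per oil. Its reason is precedent: "This is based on previous studies which have investigated interventions for perceived muscle soreness". Those studies, for which one citation is given, are said to have "utilized a similar sample size for a power of 80% and a 1 tailed level of significance of p<0.05". The section states no effect size, SD, correlation, comparison or time point. Section 1.4 (Preliminary Data) is marked as not applicable.

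The whole analysis plan is two sentences in 6.1: "Treatment analysis will involve a 1-way repeated measures ANOVA" and "Differences will be considered significant when p values are below an alpha level of 0.05". No factor, contrast or tail is named.

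The aims in 1.1 are to see how the oils "impact delayed onset muscle soreness after eccentric exercises compared to one another and to control". The hypothesis is directional only against control: each oil "will reduce perceived muscle soreness in subjects compared to control".

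On the design, 1.3 says: "Each subject will have one upper extremity serving as the control, and one upper extremity which receives the intervention". Soreness is recorded "for both the intervention and control upper extremity at 24, 48, and 72 hours post-exercise". Oil versus control is thus a within-subject comparison, and oil versus oil is a between-subject comparison of 10 v 10.

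**The concern.** The power figure and the planned test do not match. An ANOVA F test takes differences in either direction as evidence, so at 0.05 it is not a one-tailed 0.05 test. The documents plan two kinds of comparison with different error structures, and 1.5 does not say which of them the 80% concerns. For oil versus oil, no direction is hypothesised that a one-tailed level could rest on, and a 1-way repeated measures ANOVA has no between-subject term with which to test it.

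At stake is how the result is read. Publication is planned (6.4). A null finding set against 80% power may be taken as evidence of no effect, when a reader cannot tell what difference 20 subjects could detect. The risk is greatest for oil versus oil. Type I error is not inflated by any of this.

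**Working it through.** **1. Can N=20 be reproduced?** No. Power depends on n, alpha, sidedness and the standardised effect. The documents give n (10 per oil), alpha (0.05) and a one-tailed level with 80% power attributed to earlier studies. They give no effect or SD, so there is nothing to recompute.

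**2. Illustration: what the change of tail does.** Assume that the one-tailed 80% carries over exactly, with one score per arm and an effect in the hypothesised direction. Let D be the treated-minus-control difference within a subject, and d the effect in SDs of D.

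- Paired test: df = n − 1, noncentrality = d√n.
- Two groups of n, comparing D: df = 2n − 2, noncentrality = d√(n/2).
- Power is the noncentral-t probability beyond t(0.95) one-tailed, or beyond ±t(0.975) two-sided. With two levels, F = t², so the F test is the two-sided test.

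| Reading | d for 80% one-tailed | Noncentrality | Critical t, one-tailed → two-sided | Two-sided power at that d |
|---|---|---|---|---|
| Paired, n=10 (one oil) | 0.853 | 0.853 × √10 = 2.70 | 1.833 → 2.262 | 67.1% |
| Paired, n=20 (oils pooled) | 0.577 | 0.577 × √20 = 2.58 | 1.729 → 2.093 | 68.7% |
| 10 v 10 (oil v oil) | 1.156 | 1.156 × √5 = 2.58 | 1.734 → 2.101 | 68.6% |

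A three-level repeated measures F test at the paired effects gives about 73% if only one level differs and sphericity holds.

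**3. Does this show power below 80%?** No. Hold d at 0.853 and change only the unstated choices, always two-sided at 0.05:

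- Oil versus oil, 10 v 10: noncentrality 0.853 × √5 = 1.91, power 44%.
- Both oils pooled against control, n=20: noncentrality 0.853 × √20 = 3.81, power 95%.
- Mean of the three time points, one oil, n=10, with 0.853 SD at each time: d becomes 0.853/√((1+2r)/3), where r is the correlation of D between times. For assumed r of 0.3, 0.5 and 0.8 this is 1.17, 1.04 and 0.92 SD, and power is 91%, 84% and 73%. It crosses 80% at r of about 0.60.

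The results lie on both sides of 80%. The first two also show that one power figure at one standardised effect cannot describe both a paired and a 10 v 10 comparison.

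**4. What the planned numbers can detect with 80% power, two-sided.**

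| Comparison | Alpha | Detectable difference (SD of D) |
|---|---|---|
| Each oil v control, 10 completers | 0.05 | 1.00 (0.996) |
| Each oil v control, 9 completers | 0.05 | 1.07 |
| Each oil v control, 10 completers | 0.025 | 1.14 |
| Oil v oil, 10 v 10, equal SDs | 0.05 | 1.33 (1.325) |

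Rounding the last figure down to 1.32 would give 79.7%, hence 1.33. The 9-completer line is there because 4.4 lets subjects leave at any point and 1.5 makes no allowance for it.

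**The case against.** The best defence is that 1.5 only reports what earlier studies did and never says that this trial has 80% power. In addition, 6.1 does not use the term two-sided, the hypothesis against control is directional, and a two-level contrast can be tested one-tailed.

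Part of this stands. There is no calculation in 1.5, so this is a gap in the sample-size justification and not an arithmetic error. Non-directionality follows from the F test, not from an explicit statement. A prespecified one-sided contrast against control would be consistent with the hypothesis in 1.1.

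But 6.1 plans no such contrast. If it did, the effect and SD would still be missing, and oil versus oil would still lack both a direction and a model. And if the 80% is not meant for this trial, 1.5 contains no power basis at all.

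It is also fair to object that every percentage under the check rests on an effect back-solved from the precedent. The design and test behind the cited 80% are not in the documents, so whether it transfers cannot be checked. The percentages therefore illustrate the mismatch and do not estimate this trial's power.

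**Conclusion.** The concern holds as a sample-size justification that does not match the analysis plan. The quoted 80% belongs to a one-tailed level that the planned test does not use, actual power cannot be derived from the documents, and one of the two stated comparisons has no term in the planned model.

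The size can be given only conditionally. If the precedent's 80% carried over exactly, a two-sided test of a single contrast would have about 67% to 69% power at the same effect. This assumes one score per arm and an effect in the hypothesised direction.

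A reader might infer that the trial is underpowered, or that it needs the 13 per oil that would restore 80% at 0.853 SD. The documents do not support that: the true effect is unstated, and equally plausible readings exceed 80%. The point should be corrected before analysis, but it does not call for more subjects.

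**What to change.** Keep N=20 and make 1.5 power the tests that 6.1 names.

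**In 6.1:** name one soreness score per arm (a prespecified time point or summary), and define D as its treated-minus-control difference for each subject. Test each oil against control with a two-sided paired t test of D at 0.05 (n=10 per oil), stated as unadjusted for two oils. Compare the oils with a two-sample comparison of D, which is equivalent to the arm-by-oil interaction, and report an estimate with 95% CI and p value.

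**In 1.5:** delete the one-tailed 80% claim and state:

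> With 10 completers per oil and two-sided alpha 0.05, each oil-versus-control paired test has 80% power for a mean difference of 1.00 SD of D (1.07 SD with 9 completers). Oil versus oil (10 v 10, equal SDs) has 80% power only for about 1.33 SD of D. N was set by precedent and feasibility.

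Add the assumed SD of D in VAS units with its source, or state that none is available. Without it, a reader cannot turn these figures into a soreness difference.

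**Cost:** wording only, with no extra subjects and no change in data collection. The stated power becomes less favourable, and the lack of multiplicity adjustment becomes explicit. Testing each oil at 0.025 instead would move 1.00 SD to 1.14 SD.

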1.6 Study Variables

A. Independent Variables, Interventions, or Predictor Variables

Independent variables are whether the subject receives topical application of *Eucalyptus globulus* oil or *Mentha x piperita* oil. Additionally, each subject will have an intervention extremity that receives the essential oil, and a control extremity which receives no treatment. The subjects will be aware of which group they are in, as there is no way to mask the fragrance.

B. Dependent Variables or Outcome Measures

The dependent variable will be self-reported perceived muscle soreness based on a visual analog scale.

1.7 Drugs/Devices/Biologics

No drugs will be used during this investigation. Essential oils are not regulated under the U.S. Food and Drug Administration. The oils obtained commercially from SunRose Aromatics.

1.8 Specimen Collection

No specimens will be collected.

1.9 Data Collection

A. Primary Data Collection

Location: Data collection will occur at the Manor Health and Rehabilitation Center ([name]). Permission has been granted by the director of this facility and by authorities with CentraState Healthcare System, which the Manor is owned by.

- Process of Data Collection: The investigators will oversee the collection of data in-person at the facility. Only Rutgers study staff will be involved in any research roles. Staff at the Manor Health and Rehabilitation will not be involved in the collection of data or treatment of subjects pertaining to this study, but will maintain their usual roles at the study site throughout the duration of this investigation.
- Timing and Frequency: Data collection will occur at the beginning of a subject's participation in order to collect demographic information, and then at 24, 48, and 72 hours following exercise to survey their perceived muscle soreness.
- Procedures for Audio/Visual Recording: There will be no recording of subjects.
- Study Instruments: Recruited subjects will complete a survey to collect demographic data, medical history, and allergies. Subjects will identify their perceived muscle soreness using a self-reported visual analog. They will complete this for both the control and intervention arm at 24, 48, and 72 hours post-exercise.
- Ethnographic Studies, Interviews, Or Observation: There will be no interviews or observational aspect to this study.
- Subject Identifiers: Each subject will be assigned to a random number associated with their name that will be stored in a password protected file on a secure drive. In a separate, also password protected, file the collected data will be stored with the associated subject's number
- B. Secondary Data Collection: No secondary data collection will occur.

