Participants will be divided equally into the *Mentha x piperita* or the *Eucalyptus globulus* group. A 2% oil mixture for topical application will be made with essential oils from SunRise Aromatics diluted in fractionated coconut oil per guidelines from the RJ Buckle Clinical Aromatherapy for Health Professionals course recommendations. Physiciansupervised eccentric exercise of the elbow flexors will be performed based on an adaptation of the method described by Weber. [14] Free weight dumbbells will provide resistance. The subject will be instructed to prolong the extension aspect of the curl to be five seconds long. They will repeat this motion for 10 or more repetitions until exhaustion, either due to the participant feeling they can no longer tolerate the five second eccentric aspect of the exercise or the investigator identifying that their form has faltered. If subjects reach exhaustion after the 10 repetitions minimum, they will rest for 1 minute. If they are unable to complete 10 repetitions at this weight, the resistance will be decreased to the next lowest weight and they will continue until exhaustion. This will continue until subjects reach exhaustion with the lowest resistance weight. Immediately following exercise, the participants will have the respective oil applied topically to their left upper extremity by the investigator. Their right upper extremity will serve as the control and no essential oil will be applied. Investigators will apply the oil without any use of massage technique and to only apply very superficial pressure. This application will be repeated 8 hours after exercise, when DOMS has been known to initiate, and at 24 hours after exercise, when DOMS may begin to peak.

Subject Safety

Vital signs will be measured prior to the initiation of exercise, including temperature, heart rate, blood pressure, and oxygen saturation. A physician will be notified of any abnormalities and the subject must be medically optimized prior to exercising. All exercise will be supervised by a physician. After the intervention is applied, subjects will be directly observed for 15 minutes by a physician to ensure no immediate adverse reactions occur. Vital signs will be repeated at the end of the observation period.

Nursing staff will be on-site in their usual capacity and physicians available on-call throughout the duration of the study. Medications are available at the facility if needed for any adverse events.

B. Data Points

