1.10 Timetable/Schedule of Events

T=0: Subjects perform supervised eccentric curl exercises.

T=1: Subjects have the intervention and control oils applied topically to their proximal arms immediately after exercise is completed and are monitored for 15 minutes.

T=1+ 8hrs: Subjects have a second application of the intervention and control oils applied topically to their arms.

T=1+ 24hrs: Subjects have a third application of the intervention and control oils applied topically to their arms. They complete the visual analog survey for perceived DOMS.

T=1+ 48hrs: Subjects complete the visual analog survey for perceived DOMS again.

T=1+ 72hrs: Subjects complete the visual analog survey for perceived DOMS for the final time.

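### No soreness score is taken before exercise, so with oil always on the left arm a mean left-right difference at entry is counted as an oil effect and cannot be detected or removed

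*Combined protocol and SAP*

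**What the plan says.** The VAS times agree wherever they are listed.

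- Section 1.3 B (Data Points): scores are "recorded by investigators for both the intervention and control upper extremity at 24, 48, and 72 hours post-exercise".
- Section 1.9 (Timing and Frequency): what is gathered at entry is demographic, and soreness is scheduled later: "and then at 24, 48, and 72 hours following exercise to survey their perceived muscle soreness".
- Section 1.10: the first entry is "T=0: Subjects perform supervised eccentric curl exercises". The next is the first application, "applied topically to their proximal arms immediately after exercise is completed and are monitored for 15 minutes". Neither entry includes a VAS. The first VAS shares the 24-hour entry with the third application, and their order is not stated.

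Before exercise, section 1.3 A (Subject Safety) provides that "Vital signs will be measured prior to the initiation of exercise"; the items it lists are temperature, heart rate, blood pressure and oxygen saturation, with no pain or soreness score. The pain monitoring in section 6.3 also begins after exercise.

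Section 1.3 A (Intervention) has "the respective oil applied topically to their left upper extremity by the investigator", with the right arm as control. Only the choice of oil is randomised. Section 1.3 D makes the VAS the sole endpoint. Section 6.1 names a 1-way repeated measures ANOVA at alpha 0.05, with no baseline term or covariate.

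**The concern.** The hypothesis in section 1.1 B is that either oil lowers soreness relative to control, and this is tested by comparing the two arms of each subject. That comparison reads as an oil effect only if the arms would otherwise have scored the same on average. Subjects are aged 50 or over and are inpatients in subacute rehabilitation or long-term care, so arm soreness at entry need not be zero, or equal on the two sides.

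Because the treated arm is the left arm in everyone, side and treatment cannot be told apart. If left arms are on average less sore at entry, an inert oil looks effective. If they are on average more sore, a real effect is hidden. Hand dominance is recorded at screening, but it does not measure soreness and is not in the analysis. A pre-exercise score cannot be recovered once a subject has exercised.

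**Working it through.** **Inputs from the documents.** 10 subjects per oil and 20 in total (1.5, 4.3); alpha 0.05 (6.1); treated side fixed (1.3 A); VAS at 24, 48 and 72 h only (1.3 B, 1.9, 1.10). There is no SD, effect size or between-arm correlation, so the sample size in 1.5 cannot be reproduced and everything below is in assumed units.

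**1. Where an entry difference goes.** For subject i, let B_i be the left-minus-right soreness difference at entry, T the oil effect and e_i the remaining variation, with mean zero. The recorded difference is D_i = B_i + T + e_i. Its mean estimates mean(B) + T. With no measurement of B_i, the two terms cannot be separated. If mean(B) = 0, the B_i only widen the spread of D.

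**2. False-positive rate with T = 0.** If the ANOVA is applied with arm as its two-level factor at one time point, F equals the square of the paired t statistic, so a two-sided paired t-test is used. Let b be mean(B) divided by the SD of D. The statistic is noncentral t with n-1 degrees of freedom and noncentrality b × √n. The critical values are 2.262 (n=10) and 2.093 (n=20).

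| b (assumed) | n | b × √n | P(two-sided p<0.05) |
|---|---|---|---|
| 0.3 | 10 | 0.949 | 13.6% |
| 0.5 | 10 | 1.581 | 29.3% |
| 0.3 | 20 (oils pooled) | 1.342 | 24.7% |
| 0.5 | 20 (oils pooled) | 2.236 | 56.5% |

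The nominal rate is 5%. In the other direction, a 0.25 SD difference working against the oil lowers one-sided power at n=10 from 80% to 54.6%.

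**3. Oil versus oil.** The contrast is mean(D) in one group minus mean(D) in the other, so a mean(B) common to both groups cancels. Simulation with a shared 10 mm difference and an SD of 20 mm gave a type I error of 5.0%.

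**4. What a baseline would do to the bias.** Assumed: SD of D 20 mm (standing part 10 mm, remainder 17.32 mm), baseline measurement error 5 mm on the arm difference, T = 0.

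- Change from baseline: for a mean entry difference of 5 or 10 mm, the simulated estimate is about 0 mm and the false-positive rate about 5%.
- Baseline difference as an uncentred covariate, effect read at a baseline difference of zero: the slope is attenuated to 10²/(10² + 5²) = 0.8, so a fraction 1 - 0.8 = 0.2 of the bias stays. That is 1 mm of 5 mm, or 2 mm of 10 mm; simulation agrees.
- Baseline difference as a mean-centred covariate: the intercept is again mean(D), so none of the bias is removed.

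**5. What a baseline would do to precision at n=10.** Let r be the correlation between the baseline and later arm differences. Each ratio is the variance relative to the analysis without a baseline.

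- Covariate, effect at zero, mean baseline difference zero: (1 - r²)(n - 2)/(n - 3) = (1 - r²) × 8/7.
- Change from baseline, equal variances at the two times: 2(1 - r).

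| r (assumed) | Covariate | Change |
|---|---|---|
| 0.3 | 1.04 | 1.40 |
| 0.5 | 0.86 | 1.00 |
| 0.7 | 0.58 | 0.60 |

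At low r, either adjustment costs precision.

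**The case against.** The strongest reply is that entry soreness may be close to zero on both sides. Upper-extremity musculoskeletal injury or weight-bearing restriction within a year is an exclusion, and so is resistance training in the past year. The score is also meant to capture soreness induced by the study exercise, which section 1.2 says often begins 8 to 24 hours after activity. This stands in part: it makes a mean difference of 0.3 or 0.5 SD less likely, and nothing in the documents supports those values. It does not dispose of the point, because chronic or current arm pain is not itself an exclusion and, without a baseline, the reply cannot be checked.

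A second reply is that the bias exists only because the treated side is fixed; with the side randomised, entry differences would be chance imbalance. That is correct. The rates above describe the combination of a fixed side and no baseline, and should not be counted again in any separate criticism of the fixed side.

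Three stronger readings are tempting and do not hold.

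- A reader might infer that every existing side difference biases the result in one direction. Only the treated side is constant; some residents may be sorer on the left and others on the right, and only the mean matters.
- A reader might infer that baseline adjustment is sure to improve precision, by r² (9%, 25% or 49% at r = 0.3, 0.5 or 0.7). Those are large-sample values that ignore estimation of the slope; at n=10 the covariate raises variance by about 4% at r = 0.3.
- A reader might infer that a score taken after exercise but before oil would serve as well. It mixes acute exercise discomfort with standing soreness, and the contrast proposed here does not use it.

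**Conclusion.** The point holds for oil versus control, which is the stated hypothesis. The schedule is explicit and supplies no baseline, so this is a design choice rather than a missing detail. A non-zero mean left-right difference at entry is estimated as oil effect, and the planned data can neither show nor correct it. The documents do not show that such a difference exists. The rates of 13.6% to 29.3% (n=10) and 24.7% to 56.5% (pooled) rest on an assumed mean difference of 0.3 to 0.5 SD and on a paired comparison at one time point. The absence of a baseline is certain; the size of the harm is not.

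A reader might also infer that the oil-versus-oil comparison is biased in the same way, or that a baseline would cure the left-right confounding. Neither follows: a shared difference cancels between the randomised groups, and a baseline removes only soreness present before exercise.

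**What to change.** - **Sections 1.3 B, 1.9 and 1.10:** add one VAS for each arm before exercise, at the time of the vital signs.
- **Section 6.1:** prespecify, as the oil-versus-control contrast, the oil-arm minus control-arm difference in change from this baseline at 24, 48 and 72 h.
- **If a covariate is preferred:** enter the baseline arm difference uncentred, evaluate the effect at a baseline difference of zero, and state that baseline measurement error leaves some bias.

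The cost is a short amendment and one extra VAS pair per subject, at a visit where investigators are already present. Some precision may be lost: under equal variances, change from baseline has a larger variance than the later score alone when r is below 0.5. The change does not address a left-right difference in the response to the exercise, which comes from the fixed treated side and needs its own remedy.
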